**Potential Benefits**

The data collected from this study will help researchers further understand the risk factors that are associated with health trajectories. By utilizing machine learning and monitoring mobile technology, genomic, and environmental data, healthcare professionals can better understand key predictors of treatment response for patients with mental health conditions. These data can lead to changes in practice and, subsequently, improve the quality of patient care. Additionally, participants may see improvement in their mental health symptoms and overall well-being as a result of engaging in the app-based interventions. Access to mHealth interventions has the benefit of expanding access to treatment and may have wider effects on the population.

Participants will also receive an Apple Watch or Fitbit free of charge, and may keep these devices following their completion of the study. With these devices, participants can benefit from the health and fitness features to improve their well-being and overall quality of life.

Some participants will gain satisfaction from contributing to research about mental health conditions, which we hope will add to our understanding of disease etiology and potential interventions. This study also provides an opportunity to explore the use of integrated health systems, electronic medical records, and patient reported outcomes as tools for research to improve healthcare.

### **STUDY SUPPORT**

The study staff will serve as the first contact point for any questions and technical issues encountered by the participant during the study. Support will be available to participants via email, phone, or scheduled in-person visits, as well as prepared supporting material (e.g., frequently asked questions within the study app). The study staff will address all study-related questions and will support participants in setting up their devices to meet study requirements. If participants have non-study related questions on using their Apple Watch or Fitbit, UM may refer them to Apple or Fitbit customer support. Participants will be recommended not to provide information on their participation in the study to customer support in order to minimize the risk of personnel identifying the study participant. If devices are broken, study staff may arrange a device swap with used or new equipment as available, or direct participants to Apple or Fitbit customer support. This study does not cover any costs associated with damages to the study devices except device shipment if swap is done via mail. Study staff will also support participants in making sure their devices are setup in a study-compliant manner, including but not limited to support to reinstall app(s) after a phone replacement or app deletion.

In the event that study staff become aware of study tasks that indicate psychiatric emergency or demonstrate critical laboratory values or pulse irregularities, study staff will respond pursuant to existing Michigan Medicine policies and generally accepted standards of care.

### **COSTS**

There are no direct costs to the participant by participating in this study. All devices and the mobile applications are provided for free. There may be an indirect cost to participate in this study because some of the data collected for this study and transmitted to the study team may need to be covered by the participant's phone data plan.

If participants are found to have any medical or psychiatric condition, they are financially responsible for any follow-up treatment sought from their health care provider.

### **STUDY TERMINATION**

The study may be terminated at any point. Participants will receive full compensation for their study task fulfillment up until the termination date. Participants will be informed of the study termination by phone, letter, or email and given contact information if they have questions for follow-up. Information will include directions on how to uninstall the study apps and reverse study-specific phone settings. Participants will no longer be contacted by study staff or receive notifications from the MyDataHelps study app. Participants will be informed of the possibility of early study termination during enrollment.

## **WITHDRAWING**

Participants may withdraw from the study at any time, which will be communicated to participants by study staff and in the electronic informed consent form. Deleting the study app does not withdraw a participant from the study. Participants who choose to withdraw prior to completing the study will have no additional data collected, but data collected prior to the date of withdrawal can be used for research or product development projects initiated after the date of withdrawal. Alternatively, participants may opt for a complete withdrawal, which constitutes a request that their previously collected data not be used for future research or product development projects. Biological specimens will be destroyed and genomic and study data and medical information will not be available for new research or product development projects that are not already in progress. However, if the data are already in use for an existing research or product development project, such data may continue to be used for this project. This message is conveyed to all participants in the electronic informed consent process. Participants can withdraw by contacting study staff by phone or email, and study staff will initiate any necessary follow-up contact with participants by letter, phone, or email to confirm withdrawal. Contact will consist of follow-up on reason for withdrawal and information on how to uninstall the study apps and reverse study-specific phone settings. Participants will no longer be contacted by study staff or receive notifications from the MyDataHelps study app.

Participants may also be withdrawn from the study by the investigators for any of the following reasons:

- a. Adverse event that renders the participant ineligible or makes it not in the best interest of the participant to continue participation in the opinion of the investigators
- b. Observed protocol violation, including being observed to no longer meet inclusion criteria, a change that renders data less usable, or loss of follow-up
- c. Observed to meet any of the exclusion criteria after enrollment
- d. Death of participant

Participants will be informed of the withdrawal by phone, letter, or email and given contact information if they have questions for follow-up. Information will include instructions on how to uninstall the study apps and reverse study-specific phone settings. Participants will no longer be contacted by study staff or receive notifications from the MyDataHelps study app. As outlined in the electronic informed consent document, participants may contact study staff if they would like to opt for a complete withdrawal, as described above.

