### **Required Device Configuration**

Participants will be guided through the study setup configuration requirements during the enrollment process. For the full study duration, participants will maintain the basic study configuration on their study devices (e.g., MyDataHelps, app-based intervention, Apple Watch or Fitbit synced with smartphone). Study staff will reach out to participants if non-compliance with study configuration is noted and will offer re-education or help to resolve technical problems. In interactions with participants, study staff will remind participants to ensure their devices are compliant with required device configuration. Notifications in MyDataHelps will support the participant in maintaining the required device configuration by sending update reminders.

A small minority of participants may experience study hardware or software problems. We may contact these participants to troubleshoot the problems via phone, letter, or email. An in-person meeting with study staff will be offered for further troubleshooting, if needed. If study tasks are completed successfully, these issues will have no effect on their compensation. However, if participants are unable to complete study tasks (e.g., follow-up surveys) due to these issues, their compensation may be impacted.

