### ***Self-Report Surveys***

Participants will complete four surveys, including a baseline survey and three follow-up surveys. All surveys will be self-administered via the MyDataHelps study app. In the case of technological difficulties, the study team does have paper copies of the baseline and follow-up surveys available, and the surveys may be administered in person or by phone. The baseline survey will take about 25 minutes. Survey questions include demographics, overall physical and mental health symptoms and diagnoses, substance use, environment, use of mobile technology and health apps, and social network and support. For each of the three follow-up assessments, participants will complete an approximate 20-minute survey with similar content as the baseline survey. If necessary, the survey can be administered by study staff via phone who will read survey questions to the participant and record their responses. When participants are due for their surveys, they will receive an email or app notification that their survey is available via the MyDataHelps app. If participants do not respond to the questionnaires, and have not indicated that they do not wish to participate in the study, a reminder will be sent by email, phone, mail, or text message.

The first follow-up survey will occur at the end of 6 weeks post-enrollment, the second at the end of 18 weeks post-enrollment, and the third at the end of 12 months post-enrollment. Each of these time-points may occur near the time of an in-person outpatient mental health clinic appointment, at which participants may be asked to answer some of the same questions that are contained in the study surveys. To reduce participant burden, study staff will monitor upcoming appointments and participants will receive a version of the survey without redundant items if they have an appointment within 1 week of their follow-up survey due date. They will still complete the remainder of the follow-up survey and be paid the same amount for their time. Additionally, participants who do not show for clinic appointments will still be able to complete the follow-up assessments via standard study procedure.

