### ***Electronic Health Record Data***

Participation in the study will allow for the use of the patients' electronic health record (EHR) data, outcomes registries (including local, state, national, and international, such as the National Death Index), prescription-related data accessed via the SureScripts Health Information Network, administrative data, and other sources of health and outcomes data stored in the University of Michigan Research Data Warehouse. Patients agree to be re-contacted in the event that researchers would like to consent the patients for additional studies requiring further testing, data, or feedback. They may decline any further study opportunities without any impact on their participation or compensation for this study.

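### Both described forms of withdrawal end all new data, so a participant who asks to stop the device, app, prompts or sensing has no stated way to keep surveys and record follow-up

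*Combined protocol and SAP*

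**What the plan says.** The WITHDRAWING section of the protocol gives a participant two options. Under the first, "Participants who choose to withdraw prior to completing the study will have no additional data collected", while data already held stay usable. Under the second, "participants may opt for a complete withdrawal, which constitutes a request that their previously collected data not be used" in future projects, and specimens are destroyed. Staff make whatever follow-up contact is needed to confirm the withdrawal, and its content is fixed: "Contact will consist of follow-up on reason for withdrawal and information on how to uninstall the study apps and reverse study-specific phone settings". After that, "Participants will no longer be contacted by study staff or receive notifications from the MyDataHelps study app".

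The same section also states: "Deleting the study app does not withdraw a participant from the study". Required Device Configuration treats a lost setup as something to repair: "Study staff will reach out to participants if non-compliance with study configuration is noted and will offer re-education or help to resolve technical problems". App-Based Interventions likewise answers non-use of the assigned app with staff contact.

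Two other provisions pull the opposite way. Inclusion criterion 7 requires willingness to keep devices, apps and settings configured throughout. Item b of the investigator-withdrawal list in WITHDRAWING allows removal of someone who no longer meets the inclusion criteria or whose change makes the data less usable.

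On follow-up that does not need the device, Self-Report Surveys says: "If necessary, the survey can be administered by study staff via phone who will read survey questions to the participant and record their responses". Electronic Health Record Data covers health records, prescription data and "outcomes registries (including local, state, national, and international, such as the National Death Index"). It ties that access to participation in the study.

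**The concern.** The study asks for three kinds of data that differ greatly in burden. The first is daily prompts, a worn device and phone sensing that may include voice and frequent locations. The second is three follow-up surveys of about 20 minutes each. The third is record and registry linkage, for which no participant task is described. Fatigue or privacy discomfort is most likely to arise from the first kind, yet formal withdrawal ends all three.

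At stake are the later survey outcomes (Table 1 schedules PHQ-9, GAD-7 and PANSI at 6 weeks, 18 weeks and 12 months) and any later event visible only in records. Aim 1 compares randomised groups, and the ANALYSIS PLAN lists t-tests and chi-square tests with no method for missing outcomes. Preventing avoidable loss is therefore the main protection that the comparison has.

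**Working it through.** The plan states no figure on this point, so the check sets the provisions side by side.

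1. **What each form of withdrawal ends.** Standard withdrawal expressly stops all additional data, with no exception for surveys or records. Complete withdrawal concerns data and specimens already held; that it also stops new data is implied rather than stated. The end of contact follows both. Neither form keeps surveys or linkage.

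2. **What happens to four kinds of participant.**
   - *Deletes the study app, or stops wearing the device, without saying so.* Still enrolled under the app-deletion sentence. Staff try to restore the setup, surveys remain due, and record access continues because it depends on participation.
   - *Stops using Headspace or SilverCloud.* Still enrolled; staff make contact to encourage use.
   - *Tells staff that they want to stop the device, prompts or sensing but would answer surveys.* No provision describes this case. The only route in the text by which a participant ends a study activity by request is withdrawal, which ends everything.
   - *Is seen by the investigators not to keep the setup.* Criterion 7 with item b permits removal, and contact then ends as well. This sits uneasily with the app-deletion sentence: one provision keeps such a person in, and the other allows them to be taken out.

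3. **A comparison within the protocol.** The Phase 2 section expressly lets participants stay enrolled if they stop outpatient care. Nothing equivalent covers stopping the device, prompts or sensing.

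4. **Scale.** The only input is the recruitment target of 4,500 (Screening and Recruitment). No withdrawal rate is given.
   - Per percentage point of formal withdrawal: 4,500 × 0.01 = 45 participants.
   - At an assumed 10%: 4,500 × 0.10 = 450.
   - At an assumed 20%: 4,500 × 0.20 = 900.

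   The 10% and 20% are assumptions chosen only to show scale. Each such participant loses between one and three follow-up surveys, depending on when they leave. The share who would accept a lesser step cannot be derived, so no count of recoverable outcomes is offered.

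5. **Arms.** App+SF and App+EF+SF carry an extra task, the intervention app with contact for non-use. EF+SF does not, but it receives dashboard and pop-up feedback that App+SF lacks. The documents do not settle which arm carries more burden.

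**The case against.** A reader might infer that anyone who drops the watch, app or daily prompts is lost to the surveys and records. The documents do not support that. The sentence immediately before the withdrawal rule says that deleting the app is not withdrawal, and non-use is met with outreach. Survey non-response brings reminders, and surveys can be given by phone or on paper. The loss described here applies only to those who formally withdraw or whom the investigators remove.

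Four further objections deserve weight.

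- **Softer exits exist.** Notifications are encouraged, not compelled, and permission is sought for phone data. This stands in part: the protocol does not say whether that permission can be refused or later revoked on its own while the rest continues. Quiet non-use brings repeated contact, so it is not an offered choice.
- **Contact at withdrawal is not guaranteed.** Staff make only such contact as is necessary, so one cannot infer that every withdrawing participant is reached. This stands, and the option must be attached to the request itself.
- **The consent form may already contain a partial option.** The consent pages were not part of the reviewed copy. WITHDRAWING says its terms are conveyed in the eConsent, which makes an extra tier there unlikely, but it cannot be excluded.
- **Bias between arms is speculative.** This also stands as a limit. Aim 1 concerns the waitlist period, generally 3 to 10 weeks, so withdrawals before the 6-week survey matter most to it. Later losses bear more on the 18-week and 12-month data and on Aim 2.

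**Conclusion.** The point holds in a narrow form. The visible text offers no step between full participation and the end of all new data for a participant who asks to stop one component, and criterion 7 with item b leaves removal of such a person to discretion. Each formal withdrawal therefore loses later surveys and linkage that might have been kept at little burden.

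The size is unknown without a withdrawal rate. Differential loss by arm is plausible but not demonstrated. The conclusion assumes that the rule against additional data covers record and registry data, as its unqualified wording implies, and that the eConsent mirrors the protocol. This is an inexpensive improvement to follow-up. It is not a defect that invalidates the randomised comparison.

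**What to change.** In WITHDRAWING, and in the eConsent if it does not already do so, separate stopping study components from withdrawing consent for follow-up. When a participant asks to withdraw, offer:

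1. stop the app, device, prompts and sensing, but keep the remaining surveys by phone or on paper;
2. stop all contact, but allow continued record and registry linkage;
3. stop all new data;
4. complete withdrawal as now described.

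Record the level, date and arm. Keep participants at levels 1 and 2 in their randomised arm for the outcome analysis. Reconcile criterion 7 and item b with the app-deletion sentence by stating in item b that stopping a component is not by itself a reason to end follow-up.

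The cost is an IRB amendment to the protocol (and to the consent wording if needed), a slightly longer withdrawal script and one tracking field. Some outcomes will also be measured after the assigned intervention has stopped, which the report should state.

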### **Phase 1**

Patients with scheduled intake mental health appointments, pre-screening mental health appointments, on the waitlist/referral list, or identified as a potential patient seeking mental health care at Michigan Medicine or University Health Services will be recruited to participate in the study. Patients can be recruited at any time between the appointment being scheduled to up to one month following their intake appointment.

Participants that are enrolled with sufficient time before their scheduled appointment ( $\geq 2$  weeks) will be randomized to one of **three groups**:

- 1) Enhanced Feedback + Standard Feedback (**EF+SF**): Participants will receive enhanced feedback from the MyDataHelps study app in addition to standard feedback from the Apple Watch health app or Fitbit activity tracker
- 2) App-Based Intervention + Standard Feedback (**App+SF**): Participants will receive an app-based intervention in addition to standard feedback from the Apple Watch health app or Fitbit activity tracker
- 3) App-Based Intervention + Enhanced Feedback + Standard Feedback (**App+EF+SF**): Participants will receive an app-based intervention, enhanced feedback from the MyDataHelps study app, and standard feedback from the Apple Watch health app or Fitbit activity tracker

Some patients may have a shorter waiting period (<2 weeks) prior to their intake appointment (e.g., due to acute mental health symptoms). These patients will also be contacted for recruitment to provide opportunity for benefit from the research and from access to the mHealth interventions and will still be randomized to one of the above-listed groups.

As part of the enrollment process, participants will be guided by a study team member through **three processes**:

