### Surveys

Participants will be asked to complete four surveys, including a baseline survey at the time of enrollment and three follow-up surveys, which will be designed to complement in-clinic assessments completed as a part of standard outpatient mental health care. To the extent possible, redundancy with in-clinic assessments (i.e., due to the Measurement-Based Care program) will be avoided. The first follow-up survey will occur at the end of 6 weeks post-enrollment, the second at the end of 18 weeks post-enrollment and the third at the end of 12 months post-enrollment.

Depending on waitlist length for outpatient mental health services, there may be variation in whether participants have engaged with clinical care by the time they complete their follow-up survey(s). Surveys will be administered by the predetermined schedule regardless of whether participants have engaged with care. The rationale for this decision, rather than scheduling follow-up surveys to coincide with the initiation of outpatient care:

1. There is a possibility that participants may never engage with outpatient care, and these non-engagers would never receive follow-up surveys
2. Waitlist time often varies between recruitment sites (i.e., UHS tends to have a shorter waitlist for care), which would create measurement biases (e.g., UHS patients may consistently engage in care with less time to engage with the app-based intervention)
3. Participants may be receiving other mental health care (e.g., via primary care), making it less important to time follow-up surveys with the initiation of outpatient mental health services
4. The existing timeline ensures all participants randomized to the groups receiving app-based interventions have received a reasonable 'dose' of the intervention prior to assessment
5. The existing timeline ensures that measurement will take place at generally the same time frame for all participants

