## **Phase 2**

Phase 2 begins when participants establish care with a clinical provider at Michigan Medicine Outpatient Psychiatry or UHS. In Phase 2, participants will engage with outpatient mental health care services as part of routine care, and the study will continue to gather both active and passive data on participants' symptoms and activity, similar to Phase 1. Participants will continue to have access to their assigned app-based intervention while concurrently receiving outpatient mental health services. The study will collect data from participants' phones and apps for up to one year following the initiation of clinical care or until participants have completed their 12-month follow-up survey. Participants may still remain enrolled in the study if they cease engagement with outpatient mental health care services during this phase.

*Summary of tasks that participants will be asked to complete during Phase 2:*

- Complete daily mental health symptom assessments via the MyDataHelps app
- Wear assigned device (Apple Watch or Fitbit) regularly for objective data collection
- Engage with assigned app-based intervention (Headspace or SilverCloud)
- Complete 6-week follow-up survey
- Complete 18-week follow-up survey
- Complete 12-month follow-up survey
- Provide a biological specimen (if not yet completed during Phase 1)

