### **Inclusion Criteria**

1. Must have a scheduled intake mental health appointment, pre-screening mental health appointment, on the waitlist/referral list, or identified as a potential patient seeking mental health care at Michigan Medicine or University Health Services
2. Age  $\geq$  18 years
3. Must have daily access to a smartphone to use for the study (iPhone 5s or later, depending on Apple Watch version available, or Android smartphone compatible with relevant Fitbit model and study app)
4. Understands English to enable consent and use of the MyDataHelps app and app-based interventions
5. Provide complete, updated contact information upon enrollment to the study
6. Agree to be contacted by study staff during the study
7. Willingness to keep study setup (devices, apps, settings) in required configuration for the duration of the study, and following instructions by study staff if required to update or re-achieve required configuration if required configuration has been lost (e.g., change of phone, app deletion)

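### Investigator withdrawal on set-up or eligibility grounds also ends survey follow-up, by a route structurally wider in the two app arms

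*Combined protocol and SAP*

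**What the plan says.** The WITHDRAWING section gives investigators a discretionary power: "Participants may also be withdrawn from the study by the investigators for any of the following reasons". Ground (b) reads "Observed protocol violation, including being observed to no longer meet inclusion criteria, a change that renders data less usable, or loss of follow-up". Ground (c) adds meeting any exclusion criterion after enrolment. No threshold or decision rule goes with either. The consequence is stated in the same section: "Participants will no longer be contacted by study staff or receive notifications from the MyDataHelps study app".

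Two other sections determine what ground (b) can reach. Item 7 of the Inclusion Criteria is "Willingness to keep study setup (devices, apps, settings) in required configuration for the duration of the study", together with following staff instructions to restore a lost set-up. Required Device Configuration says that "participants will maintain the basic study configuration on their study devices (e.g., MyDataHelps, app-based intervention, Apple Watch or Fitbit synced with smartphone". The intervention app is thus part of the required set-up. EF+SF has no such app; its description under Phase 1 is "Participants will receive enhanced feedback from the MyDataHelps study app in addition to standard feedback", and every arm installs MyDataHelps.

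Elsewhere the protocol aims to retain people. The Surveys section fixes the survey dates partly for this reason: "There is a possibility that participants may never engage with outpatient care, and these non-engagers would never receive follow-up surveys". Phase 2 says: "Participants may still remain enrolled in the study if they cease engagement with outpatient mental health care services during this phase".

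**The concern.** Stopping an intervention and leaving follow-up are different events, and the withdrawal text does not separate them. A participant who drops the assigned app and declines to reinstall it can be brought under ground (b). Surveys that could still have been obtained are then never requested.

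Aim 1 compares the effectiveness of the interventions. If more people leave this way from App+SF and App+EF+SF than from EF+SF, and their outcomes differ from those of people who stay, the contrasts against EF+SF are distorted. The contrast between the two app arms lacks this asymmetry, since both carry the extra component. The ANALYSIS PLAN proposes t-tests and chi-square tests and says nothing about analysis population or missing data, so nothing planned would correct the loss.

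The documents describe no blinding, and staff guide the app download, coach SilverCloud users and contact non-users. That those who decide on withdrawal would know the arm is a reasonable inference, though it is not stated.

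**Working it through.** **Textual chain**

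1. Ground (b) includes no longer meeting an inclusion criterion. Item 7 is such a criterion and covers apps.
2. The required configuration names the intervention app. Lasting refusal to restore it can count as failing item 7, or as a change that makes the data less usable.
3. Only two of the three arms have that component, so there is one more way to meet the ground in those arms.
4. Self-Report Surveys delivers surveys through MyDataHelps with staff reminders, and has phone and paper as back-up. Once staff contact and app notifications end, all of these routes close for the surveys still due.

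**Size, on assumed inputs**

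The only planning figure is 4,500 participants. It comes with no allocation ratio, SD, effect size, power or dropout rate, so it cannot be reproduced; the point does not depend on it. Equal allocation is assumed: 4,500 / 3 = 1,500 per arm.

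Let *w* be the share withdrawn in an arm and *d* the amount, in SD, by which withdrawn participants would have scored worse than retained ones. The full-arm mean is the retained mean plus *w* × *d*, so completers understate it by *w* × *d*. Hence

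bias in the completer difference = (*w*_app − *w*_EF) × *d*.

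The standard error in SD units is √[1/(1500(1 − *w*_EF)) + 1/(1500(1 − *w*_app))]. Type I error is for one app arm against EF+SF, two-sided 5% test, normal approximation, no true difference. For scale, the difference detectable with 80% power is (1.960 + 0.842) × √(2/1500) = 0.10 SD.

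| Withdrawn, EF+SF vs app arm | Bias (SD), *d* = 0.2 to 0.5 | Type I error |
|---|---|---|
| 2% vs 5% | 0.006 to 0.015 | 5.3% to 6.9% |
| 5% vs 10% | 0.010 to 0.025 | 5.8% to 10.1% |
| 5% vs 15% | 0.020 to 0.050 | 8.1% to 25.4% |
| 10% vs 20% | 0.020 to 0.050 | 8.0% to 24.3% |
| 10% vs 10% | 0 | 5.0% |

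Worked line: at 5% vs 15% and *d* = 0.5, 75 and 225 people are missing and the bias is 0.10 × 0.5 = 0.05 SD, about half the detectable difference. If the PHQ-9 SD were 5 to 6 (an assumption), that is 0.05 × 5 = 0.25 to 0.05 × 6 = 0.30 points.

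If *d* is negative, for instance because people drop the app once they feel better, the bias has the same size and the opposite sign.

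**The case against.** The strongest reply is that the protocol's ordinary response to lost set-up is help. Required Device Configuration has staff make contact and assist, and the only consequence it states concerns payment. App-Based Interventions answers non-use with contact. Study Support offers help with reinstalling, and WITHDRAWING says that deleting the study app is not itself a withdrawal. All of this stands and makes withdrawal less likely. It does not say what happens when help fails, and at that point the discretionary power applies without a rule.

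A reader might infer more than the documents support:

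- *Stopping the app means leaving the trial.* Loss of set-up is not a named ground. It enters only through item 7 or the data-usability wording.
- *Item 1 of the inclusion criteria fails for everyone after intake.* Phase 1 allows recruitment up to a month after intake, and Phase 2 follows people in care. Item 1 is also broad. People who leave the waitlist are largely protected by Surveys and Phase 2, so what remains is a tension in wording.
- *One missed survey leads to withdrawal.* Self-Report Surveys provides for reminders. The term for loss to follow-up is undefined, but nothing equates it with a single miss. People truly lost have missing outcomes anyway; for them the rule only ends attempts at recovery.
- *Non-users vanish from the data, so feasibility is overstated.* Nothing removes data gathered before an investigator's withdrawal unless the participant asks for complete withdrawal. Nor does the text say that health-record data stop in that case.
- *The sentence on deleting the study app contradicts ground (b).* It says only that deletion is not itself withdrawal; the investigators' power is separate.
- *The bias favours the apps.* Neither its sign nor its size can be derived from the documents, and extra staff contact in the app arms could offset the asymmetry.

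**Conclusion.** The point holds in a limited form. The text permits obtainable survey outcomes to be given up on grounds related to adherence, by a route with one more entry in the app arms than in EF+SF, and the analysis section has no stated remedy. It also sits uneasily with the plan's intention to keep surveying and retaining people who do not engage with care.

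The size is unknown. It is negligible if few are withdrawn, and could matter if withdrawal differs by about 10 percentage points between arms. That rests on assumed withdrawal shares, assumed outcome gaps and equal allocation. The case for acting is that the change is cheap and that surveys never requested cannot be recovered at analysis; it does not rest on a demonstrated bias.

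**What to change.** In WITHDRAWING, separate stopping the intervention or device set-up from ending survey follow-up:

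- State that loss of configuration, non-use of the app or device, a phone change, leaving the waitlist or a missed survey does not by itself end follow-up.
- Record such participants as off intervention or off device, with date and reason. Keep them in their randomised arm and continue the scheduled surveys by app, or by the phone or paper routes already in Self-Report Surveys.
- Keep as exceptions participant withdrawal, death, inability to give or maintain consent, and the existing best-interest judgement in ground (a), unchanged.
- Define loss to follow-up, and reconcile grounds (b) and (c) with Surveys, Phase 2, Inclusion Criteria and Required Device Configuration. Clinical decisions about participation stay with the investigators.
- In the ANALYSIS PLAN, state analysis as randomised, a missing-data method with a sensitivity analysis, and reporting of withdrawals by arm and reason.

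If everyone so flagged were surveyed and analysed as randomised, the bias from this rule would be zero in every scenario tabulated. Some will not respond, so in practice it would be reduced.

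The cost is protocol wording, a status field in the tracking database, some extra reminders and survey payments, and some participants with surveys but no passive data.
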